Short-Form Health Survey-12 (Ware et al., 1995). The SF-12 is a health-related quality-of-life questionnaire consisting of twelve questions that measure eight health domains to assess physical and mental health. Physical health-related domains include General Health (GH), Physical Functioning (PF), Role Physical (RP), and Body Pain (BP)

Total Nasal Symptom Score. The Total Nasal Symptom Score (TNSS) is the sum of scores for each of nasal congestion, sneezing, nasal itching, and rhinorrhea at each time point, using a four point scale (0–3), where 0 indicates no symptoms, a score of 1 for mild symptoms that are easily tolerable, 2 for awareness of symptoms which are bothersome but tolerable and 3 is reserved for severe symptoms that are hard to tolerate and interfere with daily activity. TNSS is calculated by adding the score for each of the symptoms to a total out of 12.

Adverse Traumatic Experiences Scale (ATES) (Kolacz et al., 2020). This measure asks about childhood adverse experiences, childhood maltreatment, other person maltreatment, life-threatening situations, sudden deaths of close ones, and personal health situations. Respondent-reported prior adverse events

of maltreatment, life-threatening situations, and sudden deaths of close ones are summed to create an adversity score (range: 0–19).

Patient Global Impression of Change (PGIC) (Hurst & Bolten (2004). The self-report measure Patient Global Impression of Change (PGIC) reflects a patient's belief about the efficacy of treatment. PGIC is a 7 point scale depicting a patient's rating of overall improvement. Patients rate their change as "very much improved," "much improved," "minimally improved," "no change," "minimally worse," "much worse," or "very much worse."

Data Analyses

Questionnaire data will be entered by participants into RedCap for researcher access. Researchers will export the data into SPSS for data analyses. All databases will be stored on password protected computers, accessible only to researchers affiliated with the study, and backed up on UNC servers.

As the current proposal is for a feasibility/pilot study, researchers will evaluate the following aims to determine whether a larger, randomized trial is warranted.

Aim 1: Examine associations between nasal congestion, autonomic functioning, adverse events, and mental health indices (depression, anxiety) at baseline. Pearson correlation analyses will be used to evaluate relationships among measures at each timepoint.

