Aim 2: (*These would be the aims for a future, randomized clinical trial, with preliminary testing using data from the current feasibility/pilot study*): Evaluate the effect of the SinuSonic on users with chronic nasal congestion. We will focus on three constructs important to psychological and physical health and hypothesize that:

- A) Nasal congestion will significantly improve when comparing baseline measures to follow-up measures at each week, and will maintain effects at 5 weeks. Repeated measures ANOVA will be used to evaluate mean change in outcome measures across time in PGIC and TNSS.
- B) Autonomic functioning will significantly improve when comparing baseline measures to end of study. Repeated measures ANOVA will be used to evaluate mean change in BPQ across time.
- C) Mental health indices (depression, anxiety) will significantly improve when comparing baseline measures to end of study. Repeated measures ANOVA will be used to evaluate mean change in HADS across time.

Aim 3: (*This would be an aim for a future, randomized clinical trial, with preliminary testing using data from the current feasibility/pilot study*). Evaluate the mediating effect of current/previous adverse experiences on outcome measures at 5 weeks, using regression models.

Aim 4: Calculate effect sizes for each outcome variable, which will be necessary to determine adequate sample size for a future clinical trial. G-Power software will be used to determine sample sizes based on the effect sizes of the current outcome measures.

References

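### Aim 2 A predicts less nasal congestion, but the ANOVA of PGIC cannot show improvement, and total TNSS cannot by itself attribute a change to congestion

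*Combined protocol and SAP*

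**What the plan says.** Aim 2 introduces its outcomes with "We will focus on three constructs important to psychological and physical health", and part A takes congestion as the first: "Nasal congestion will significantly improve when comparing baseline measures to follow-up measures at each week", with the effect maintained at week 5. The only analysis given for part A is "Repeated measures ANOVA will be used to evaluate mean change in outcome measures across time in PGIC and TNSS".

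Description of Measures defines the two variables:

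- **TNSS:** "The Total Nasal Symptom Score (TNSS) is the sum of scores for each of nasal congestion, sneezing, nasal itching, and rhinorrhea". Each symptom is scored 0 to 3, and the score is found by "adding the score for each of the symptoms to a total out of 12".
- **PGIC:** a seven-point scale giving the patient's "rating of overall improvement", from very much improved to very much worse. Steps 4 and 5 describe it as covering activity limitations, symptoms, emotions and quality of life.

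Steps 3 to 5 list TNSS at week 0 and at the end of weeks 1 to 5. PGIC is listed at the end of weeks 1 to 5 only. The congestion VAS in Step 1 is an entry criterion (5 or higher) and is in no later list.

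Aim 4 then says "Calculate effect sizes for each outcome variable, which will be necessary to determine adequate sample size for a future clinical trial", and adds: "G-Power software will be used to determine sample sizes based on the effect sizes of the current outcome measures".

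**The concern.** The hypothesis is about one symptom, compared with baseline. Neither named variable, analysed as stated, answers exactly that question.

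The PGIC problem is the more serious. Each rating already expresses change since the start, so the evidence of improvement is how far ratings lie from 'no change'. A test of differences between weeks discards that information. The outcome the hypothesis predicts, a benefit that appears and is held, would be reported as non-significant, while a waning benefit would be reported as significant.

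The TNSS problem is one of attribution. A fall in the total may come from congestion, from sneezing, itching or rhinorrhea, or from all of them. If only the total is analysed, a statement about congestion is not supported by that result alone. If the item is examined later without having been named, the choice between item and total is made with the data in view.

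**Working it through.** **Inputs from the document.** Four TNSS items, each 0 to 3; PGIC with seven categories at five times (weeks 1 to 5); TNSS at six times (weeks 0 to 5); 50 participants in one group. The document gives no SD, correlation, expected change or dropout rate, so every such value below is an assumption.

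**TNSS range.** 4 × 3 = 12, which reproduces the stated maximum. Congestion's share is 3/12 = 25%. The total can fall by up to 12 − 3 = 9 points with no change in congestion.

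**PGIC in a repeated measures ANOVA.** The numerator of the test is SS(weeks) = n Σ (week mean − grand mean)². Adding a constant to every rating leaves it unchanged, so the position of the ratings relative to 'no change' plays no part. Code the categories 1 to 7 in the listed order (assumed), so that 'much improved' = 2 and 'no change' = 4:

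- Steady at 2, or steady at 4: every week mean equals the grand mean, so in expectation there is no week effect in either case.
- Fading from 2.07 to 2.81, taken as evenly spaced (step 0.185): SS = 50 × 0.185² × (4 + 1 + 0 + 1 + 4) = 17.1. With SD 1 and within-person correlation 0.6, the noncentrality is 17.1/0.4 = 43; with correlation 0.3 it is 17.1/0.7 = 24. On 4 and 196 df, these give power of about 1.00 and 0.99.

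Simulation (n = 50, SD 1 before rounding to categories, correlation 0.3 or 0.6, 4,000 runs) agrees:

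| True pattern, weeks 1 to 5 | Probability ANOVA is significant |
|---|---|
| Steady 'much improved' | 0.043 to 0.045 |
| Steady 'minimally improved' | 0.042 to 0.045 |
| Steady 'no change' | 0.040 to 0.044 |
| Fading, 2.07 to 2.81 | 1.00 at correlation 0.6 (0.98 to 1.00 over repeat runs) |

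Repeat runs of the steady patterns gave 0.03 to 0.06, which is the nominal level.

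Compare a one-sample test against 4, with standard error 1/√50 = 0.141. A steady mean of 2 gives t = −2/0.141, about −14. A steady mean of 4 has an expected difference of zero. The fading pattern gives about −13.6 in the first week (−1.93/0.141) and −8.4 in the last (−1.19/0.141), so it is correctly read as improvement throughout. If the proportion improved is reported instead, a rate of 50% has a Wilson 95% CI half-width of 0.13 with 50 participants, or 0.15 with an assumed 40 completers.

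**Congestion item against total TNSS.** Assume the SD of change is 0.9 for congestion and 0.9 or 0.5 for each other item, with correlation of changes 0, 0.3 or 0.5. Then SD(total) = √(sc² + 3so² + 2ρ(3·sc·so + 3so²)), where sc is the congestion SD and so the SD of each other item. This gives 1.800, 2.481 and 2.846 when so = 0.9, and 1.249, 1.679 and 1.913 when so = 0.5. Simulated six-week ANOVA, n = 50, with Greenhouse-Geisser correction:

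| Assumed change | Item significant | Total significant |
|---|---|---|
| Congestion only, 0.5 | 0.98 | 0.17 to 0.79 |
| Other three only, 0.3 each | 0.04 | 0.56 to 1.00 |
| All four, 0.5 each | 0.98 to 0.99 | 1.00 |

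For week 5 against baseline, with congestion improving by 0.5, the item's standardised change is 0.5/0.9 = 0.556. The total matches it when each other item improves by (0.556 × SD(total) − 0.5)/3, which is 0.07 to 0.36 points. Above that, the total is the more powerful measure.

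**Aim 4.** Suppose a standardised change of 0.5 per item, equal SDs, and that value used as the difference between arms in a two-arm trial at 80% power: n per arm = 2(1.960 + 0.842)²/d² = 15.70/d². From the item, n = 63. From the total, with ρ = 0, 0.3 or 0.5:

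- Only congestion changes: d = 0.5/√(4 + 12ρ) = 0.25, 0.18, 0.16, so n = 252, 478, 628.
- All four items change: d = 4 × 0.5/√(4 + 12ρ) = 1.00, 0.73, 0.63, so n = 16, 30, 40.

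The two effect sizes are not interchangeable, and the error can run either way.

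**The case against.** The strongest reply is that TNSS is plainly the protocol's chosen congestion measure. It includes congestion, it has a week 0 value, and a composite nasal score is a reasonable choice that is often more powerful than one coarse item. That stands. A reader might infer that hypothesis A is not tested at all, or that total TNSS is the wrong outcome; the document supports neither. What remains on TNSS is narrower: the total supports a statement about nasal symptoms, and the item is needed for one about congestion.

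It would also be too strong to say that PGIC was left out at week 0 by oversight. A change rating has no baseline by nature. The fault lies in the test applied to it, not in the schedule.

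Nor does the document show that Aim 4 will mis-size the next trial. Aim 4 covers every outcome variable, and no primary outcome for that trial is named. If it is total TNSS, the total's effect size is the right input. The harm arises only if the next trial's outcome is congestion.

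The power contrasts come from deliberately one-sided patterns, with normal errors standing in for a four-level item. They show what is possible, not what is likely. Finally, Aim 2 is labelled preliminary testing in a pilot, and the item data will exist anyway. That lowers the stakes, but effect sizes are a stated product of the pilot, and naming the item now avoids a choice made after seeing the data.

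**Conclusion.** The point holds in two parts of unequal weight.

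1. The repeated measures ANOVA of PGIC cannot test improvement. This follows from the form of the test and needs no assumed value. The simulated rates (about 0.05 for any steady rating, 0.98 to 1.00 for a fading benefit) illustrate it under assumed coding, SD and correlations.
2. A change in total TNSS cannot by itself be attributed to congestion, which is at most 25% of the score, and no analysis of the congestion item is named. This is a modest gap in specification, not an invalid outcome. Its effect on significance or on a future sample size depends on SDs, correlations and symptom patterns that the document does not give.

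The change should be made, because it costs nothing and lets the study answer the question it poses. No gain in power is claimed for the item.

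**What to change.** **Aim 2 A, PGIC.** Remove it from the repeated measures ANOVA. For each of weeks 1 to 5, report the number and percent in each of the seven categories and the proportion improved (any category better than 'no change') with a 95% CI. A one-sample test against 'no change' is an acceptable alternative.

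**Aim 2 A, TNSS.** Name the congestion item (0 to 3, weeks 0 to 5) as the measure that supports statements about congestion. Report total TNSS beside it, labelled overall nasal symptoms.

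**Aim 4.** Give effect sizes for both, so that the future trial can use the one that matches its outcome. State that the item's before-after change may be inflated by regression to the mean, because entry requires a congestion VAS of 5 or higher and there is no control group.

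**Cost.** Wording only: no new data, participants or questionnaires. The drawback is that a 0 to 3 item is coarse and can have less power than the total when the other symptoms also improve, which is why both are reported.

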Effects of SinuSonic on Psychological and Physical Well-Being

NCT number NCT06268730
Document Date 12/26/2023

Effect of the SinuSonic Device on Psychological and Physical Well-Being in Adults with Nasal/Sinus Congestion
PI (UNC): [name]

Brief background: Chronic nasal congestion impacts the functioning of the ventral vagal complex (VVC), which includes cranial nerves of the face and head (special visceral efferents), along with vagal regulation of the heart and lungs. Physiological compromise of the VVC due to a current or previous adverse experience may allow for worsening nasal congestion, which then has a circular impact back to poorer vagal regulation of the lungs.

This chronic cycle of congestion and poor vagal regulation can likewise impact mental health. Defensive symptoms/behaviors, such as anxiety and depression, are common emergent symptoms of a compromised VVC.

Purpose: The first aim of the study is to evaluate relationships between current/previous adverse events, degree of nasal congestion, perception of autonomic regulation and symptoms of anxiety and depression via self-report questionnaires.

The second aim of the study is to evaluate the effect of the SinuSonic on physical and psychological well-being in individuals with chronic nasal congestion. The SinuSonic is a self-applied nasal device designed to enhance physical well-being by reducing nasal congestion via simultaneous administration of acoustic vibration and gentle oscillating expiratory pressure. The vibration and expiratory pressure stimulate several cranial nerves that are included in the ventral vagal complex (VVC), including the cranial nerves of the face and head (special visceral efferents). According to the Polyvagal Theory (Porges, 1995, 1998, 2001, 2003, 2007), when the VVC is stimulated, the functioning of related cranial nerves and emergent behaviors should improve, supporting a calmer, more regulated nervous system, and improved mental health.

To evaluate the effects of the SinuSonic, self-report questionnaires will be administered (via RedCap) prior to beginning use of the SinuSonic, weekly during directed use of the SinuSonic (2 minutes per day, 2 times per day), and after 5 weeks of use of the SinuSonic. Weekly self-report questionnaires will include amount of SinuSonic usage and degree of nasal congestion. The final, 5-week questionnaires will include degree of nasal congestion, perception of autonomic regulation and symptoms of anxiety and depression.

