As this is a feasibility/pilot study, data from the study will be used to estimate effect sizes and inform a larger, randomized trial on the effects of the SinuSonic on individuals with compromised autonomic regulation, if warranted by the results.

Background: The SinuSonic was developed as a non-pharmaceutical device aimed to reduce nasal congestion via simultaneous administration of acoustic vibration and gentle oscillating expiratory pressure. Previous studies have demonstrated significant improvements in congestion and ease of breathing after immediate use of the device (Cairns & Bogan, 2019) and after twice daily use for 5-weeks (Soler et al., 2020). In this study, there was significant improvement in peak nasal inspiratory flow after only 2 weeks of use, and significant improvement in multiple self-report measures of congestion after 5 weeks of use. No adverse effects were reported. A review report by Schlosser, Salley and Soler likewise concluded that the device may improve pregnancy-related rhinitis, which may be particularly important for individuals who would prefer non-pharmacological interventions while pregnant or breastfeeding (<https://sinusonic.com/blogs/learn/pregnancy-rhinitis.>)

[figure not shown]
There are common clinical symptoms, such as anxiety and depression, that are frequently associated in individuals who feel unhealthy. The Polyvagal Theory (Porges, 1995, 1998, 2001, 2003, 2007) provides a model for which these psychological and physical symptoms may be viewed as the predictable consequences of a common neural substrate. This neural substrate involves the neural regulation of the heart and lungs, as well as neural regulation of the muscles of the face and head which function together as a Ventral Vagal Complex (VVC).

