The VVC is based on the documented neuroanatomical and neurophysiological pathways between the brainstem areas that regulate the muscles of the face (via special visceral efferent pathways) and the heart and lungs (via the vagus). Features of the VVC may serve as a clinical checklist converging on symptoms of anxiety and depression as observed in several clinical disorders including autism (Bal et al., 2010; Patriquin et al., 2011; Porges et al., 2012; Van Hecke et al., 2009), Fragile-X-Syndrome (Heilman et al., 2011), selective mutism (Heilman et al., 2012), prematurity (Doussard-Roosevelt, et al., 1997), prenatal exposure to opiates and alcohol (Suess et al. 1997), PTSD (Sahar et al., 2001), perpetrators of domestic abuse (Umhau et al., 2002), Borderline Personality Disorder (Austin et al., 2007), behavioral regulation problems (Dale et al., 2011), and abuse and neglect (Dale et al., 2009). However, relating symptoms of anxiety and depression to an illness that impacts the functioning of the VVC (i.e., nasal congestion impacts the functioning of the vagus at the lungs) is a novel aspect of the current study.

Additionally, individuals who already have a compromised VVC due to adverse events (history or current), may also be at risk for the continued cycle of VVC complications (i.e., chronic congestion, anxiety and/or depression).

In summary, the function of the SinuSonic (i.e., reducing nasal congestion while improving vagal regulation of the lungs) align with the theoretical principles of the Polyvagal Theory. Thus, our proposed research will serve to determine whether the SinuSonic will have a significant impact on the reduction and management of physical and psychological symptoms (i.e., anxiety and depression), as they are described within the context of a dysregulated VVC.

Flowchart of Research Procedures:

Participants

50 adults (aged 18-99 years) with self-reported nasal congestion will be recruited for the study. Participants must be US residents.

Data Collection Procedures

Step 1: Recruit/Eligibility Screening

Individuals who make a purchase of the SinuSonic device will receive a recruitment flyer in the shipping box for their device, but only new users of the SinuSonic will be eligible to participate. The recruitment flyer will contain a QR code that users can scan to access the Eligibility Screening for the study in RedCap. Staff at SinuSonic has agreed to include the recruitment flyer when shipping packages.

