The Eligibility Screening will consist of the following questions:

- 1) Are you between ages 18-99 years old? [YES TO QUALIFY]
- 2) Have you ever used the SinuSonic device? [NO TO QUALIFY]
- 3) Do you meet any of the conditions listed under the Safety and Warnings for use of the SinuSonic device? [NO TO QUALIFY]
 - a) Current or history of breathing problems (i.e., asthma, chronic obstructive pulmonary disorder (COPD), chronic bronchitis, emphysema, pneumonia, pleural effusion, lung cancer, cancer of the throat or upper airway)

- b) Current or history of circulatory problems (i.e., active nose bleed, heart arrhythmia, coronary artery disease, congestive heart failure, heart attack)
- c) Other conditions, specified as brain tumor, moderate to severe ear pain, fever greater than 101 degrees

- 4) Have you experienced symptoms of nasal congestion that have persisted at least 2 weeks? [YES TO QUALIFY]
- 5) Is your current level of nasal congestion at 5 or higher? (VAS included here) [YES TO QUALIFY]

Step 2: Consent/Linkage File

When all eligibility criteria are met, individuals will be invited to access the Informed Consent document (also provided via RedCap) to read and e-sign. Phone number and email address for the researcher will be provided in the event of questions or request for clarification.

After receiving the e-signed informed consent, researchers will assign a SubjectID number so that the participant can use the SubjectID number when completing all questionnaire assessment sessions using RedCap. Researchers will maintain a database linking SubjectID and name on their password-protected computers that will not be accessible to anyone who is not affiliated with the research.

Step 3: Pre-SinuSonic assessment

Participants will be asked to complete this assessment, via RedCap, prior to beginning use of the SinuSonic. Researchers will provide participants with a link to the assessment (text or email), along with their unique SubjectID number to use. The following instruments will be programmed into RedCap for completion:

Prior to SinuSonic Use (week 0):

- 1) Demographic Information Form
- 2) SF12 to assess overall health ("how you feel and how well you are able to do your usual activities")
- 3) TNSS to assess current nasal symptoms
- 4) BPQ to reflect perception of autonomic regulation
- 5) HADS to assess anxiety and depression
- 6) ATES to assess history of trauma/adverse events

Step 4: SinuSonic Use / Weekly assessments

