After completing the pre-SinuSonic assessment, researchers will inform participants to begin directed use of the SinuSonic (2 minutes per day, 2 times per day). Participants will be asked to confirm SinuSonic use on a weekly questionnaire. Additionally, participants will be asked to complete the following questionnaires approximately 5 minutes after final SinuSonic use for that week. The following instruments will be programmed into RedCap for completion:

Weekly, for 4 weeks (end of week 1, 2, 3, 4).

- 1) TNSS to assess current nasal symptoms
- 2) PGIC to reflect change in activity limitations, symptoms, emotions and overall quality of life

Step 5: Final research assessment

Participants will be asked to confirm use of the SinuSonic on a weekly questionnaire. Additionally, participants will be asked to complete the following questionnaires approximately 5 minutes after final SinuSonic use on the 5th consecutive week. The following instruments will be programmed into RedCap for completion:

End of Study (end of week 5).

- 1) TNSS to assess current nasal symptoms
- 2) PGIC to reflect change in activity limitations, symptoms, emotions and overall quality of life
- 3) BPQ to reflect perception of autonomic regulation
- 4) HADS to assess anxiety and depression

Description of Measures

Body Perception Questionnaire (BPQ) (Cabrera et al., 2018). The Body Perception Questionnaire (BPQ) is a self-report measure of body awareness and autonomic reactivity. Its items are based on the organization of the autonomic nervous system (ANS), a set of neural pathways connecting the brain and body. These pathways send information from the body about the status of organs and tissues (i.e., afferent projections). Some of these incoming signals form a basis for the subjective awareness of the body. The ANS also carries signals that control the functions of these organs and tissues (i.e., efferent projections). These signals can alter the functions of the body, depending on internal and external needs. Only the Autonomic Reactivity subscale will be distributed and used for the current study.

Hospital Anxiety and Depression Scale (HADS) (Zigmond & Snaith, 1983). HADS is a fourteen-item scale with seven items each for anxiety and depression subscales. Scoring for each item ranges from zero to three. A subscale score >8 denotes anxiety or depression.

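### Aim 3 calls adverse experiences a mediator of week-5 outcomes, but the only adversity score is taken once, before first device use, so it can be a baseline predictor and not a mediator of a device effect

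*Combined protocol and SAP*

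**What the plan says.** Aim 3, under Data Analyses, is "Evaluate the mediating effect of current/previous adverse experiences on outcome measures at 5 weeks, using regression models". An italic note labels it an aim for a future randomized trial, with preliminary testing in this pilot. It states no exposure, no paths and no interaction term. Aim 2, just before it, is about the effect of the device.

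The Participants section plans that "50 adults (aged 18-99 years) with self-reported nasal congestion will be recruited for the study", and everyone enrolled is directed to use the device. Step 1 says that "only new users of the SinuSonic will be eligible to participate".

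Adversity is listed in one place, the week-0 instruments of Step 3: "ATES to assess history of trauma/adverse events". Of that session the plan says "Participants will be asked to complete this assessment, via RedCap, prior to beginning use of the SinuSonic". Description of Measures scores ATES as a sum of earlier events, range 0 to 19.

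The Purpose section adds that "Weekly self-report questionnaires will include amount of SinuSonic usage and degree of nasal congestion", and gives the reason for the pilot: "data from the study will be used to estimate effect sizes and inform a larger, randomized trial".

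**The concern.** A mediator lies on the path from exposure to outcome: the exposure changes it, and it in turn changes the outcome. A score fixed before the exposure begins cannot hold that place. Aim 3 gives the role to such a score.

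What is at stake is interpretation. If participants with more adversity have higher or lower week-5 scores, the wording of Aim 3 invites a report that adversity mediates the benefit of the device. Because the aim is marked for the randomized trial, the same label could be taken up there, where the answerable question is whether adversity modifies the treatment effect.

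**Working it through.** There is no figure in the plan to reproduce: neither the target of 50 nor Aim 3 comes with a power or precision calculation. The check is mainly a comparison of passages.

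**1. Where adversity is measured**

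| Assessment | Instruments listed | ATES? |
|---|---|---|
| Week 0, before first use (Step 3) | Demographics, SF-12, TNSS, BPQ, HADS, ATES | Yes |
| Weeks 1 to 4 (Step 4) | Confirmation of use, TNSS, PGIC | No |
| Week 5 (Step 5) | Confirmation of use, TNSS, PGIC, BPQ, HADS | No |

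Any current experience that Aim 3 has in mind is therefore recorded only before treatment.

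**2. The mediation path.** In the usual definition the indirect effect is *a* × *b*, where *a* is the effect of the exposure on the mediator and *b* is the effect of the mediator on the outcome given the exposure.

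- *Before against after, in this pilot.* Each participant has one ATES value, so its change is 0, *a* = 0 exactly, and *a* × *b* = 0 whatever *b* is.
- *Amount of use as exposure.* Use varies and is recorded weekly. But use in weeks 1 to 5 cannot alter a score taken at week 0. A correlation between the two would have to run from adversity to use, or come from a common cause.
- *Randomized trial with ATES before treatment.* Allocation is independent of ATES, so the expected *a* is 0, and any observed difference is chance imbalance.

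An illustration of the last case used 5,000 simulated trials at each size, with an assumed prognostic effect of 0.5 and an assumed device-by-adversity interaction of 0.5. The mean *a* × *b* was −0.0004 at N = 50 and −0.0005 at N = 200. The *a* path was significant in 5.6% and 5.1% of trials, which is chance level. The interaction term recovered its true value (means 0.494 and 0.500). These values are assumptions. They show which model answers the question and do not size the error.

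**3. Moderation in this pilot.** Let T be 1 with the device and 0 without, and let M be ATES. The moderation model is

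Y = β0 + β1·T + β2·M + β3·T·M.

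Here T = 1 for everyone, so it collapses to

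Y = (β0 + β1) + (β2 + β3)·M.

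Only the sum β2 + β3 can be estimated. The prognostic part (β2) and the modifying part (β3) cannot be separated without a control group.

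**4. What the data can support.** TNSS, BPQ and HADS are collected at weeks 0 and 5, so ATES can be related to the week-5 score with the baseline score taken into account. PGIC is itself a rating of change and has no baseline. For the others, two models are available:

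- Baseline-adjusted: Y5 = α + β·Y0 + γ·M
- Change score: Y5 − Y0 = α′ + γ′·M

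Subtract Y0 from the first and let δ be the slope of Y0 on M. In least squares γ′ = γ + (β − 1)·δ. The two ATES coefficients agree only if β = 1 or δ = 0. Aim 1 looks for baseline associations of adversity with congestion, autonomic function and mood, so δ = 0 cannot be presumed. The models answer different questions and may disagree.

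**5. Precision, as illustration only.** With one covariate, the half-width of a 95% interval for a partial correlation near 0 is tanh(1.96/√(n − 4)). For n = 50 (the recruitment target) it is tanh(1.96/√46) = 0.28. For n = 30 (an assumed number of completers) it is tanh(1.96/√26) = 0.37. This says how loosely any ATES association would be estimated. It does not bear on mediator against predictor.

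**The case against.** The strongest reply is that Aim 3 never says adversity mediates *the device effect*. It speaks of an effect on week-5 outcomes and names only regression. A plain regression of those outcomes on ATES fits the sentence and is close to what is recommended below. The background also treats adversity as something that precedes vagal compromise. On this view the defect is one wrong word and an unspecified model. Much of that stands, and it is why the point is minor. The word still needs to change: no exposure other than the device suggests itself, and no coherent model with ATES as mediator is stated.

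The word may be a slip for *moderating*. That would not rescue the analysis here, because no interaction is specified and there is no control group. Other mediation models could be built, such as ATES as exposure and BPQ change as mediator, but Aim 3 does not describe them.

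A reader might infer more than the documents support:

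- *That a false mediation claim will follow.* A formal mediation test should fail at the *a* path apart from chance. The harm needs an analyst to call a plain association mediation.
- *That the error will pass into the randomized trial.* The label on Aim 3 makes this possible, but that trial is conditional on the pilot results and its protocol is not before us.
- *That the pilot's effect sizes or the next sample size are compromised.* Aim 4 sizes the next trial from the outcome effect sizes, and Aim 3 does not enter.
- *That silence on the baseline score is an error of the same kind.* It is a separate gap in an exploratory aim, and neither model above is right in all circumstances. False-positive rates for either depend on correlations the documents do not give, so none is offered as the size of this point.

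**Conclusion.** Wrong as written, and minor. The conclusion rests on three facts in the plan: ATES is the only adversity measure, it is taken once before first use in new users, and it sums prior events. It also rests on one reading, that the device is the intended exposure, which the order of the aims supports but the text does not state. Given these, ATES cannot mediate a device effect here, nor in a randomized trial that measures it before treatment, and this pilot cannot show that it moderates one. The error has no numerical size. It is confined to the interpretation of one exploratory aim; no primary estimate or sample size depends on it. None of this says that adversity is unimportant: it may predict outcomes, and it may prove a moderator once there is a comparison group.

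**What to change.** 1. In Aim 3, replace the mediation wording with: *association of baseline adversity (ATES), as a baseline predictor, with week-5 outcomes*.
2. For TNSS, BPQ and the two HADS subscales, take account of the baseline score already collected. Say which model is used, and state that baseline-adjusted and change-score models answer different questions and can disagree.
3. For PGIC, relate the week-5 rating to ATES without a baseline term, and say how its seven ordered categories are modelled.
4. Report every ATES coefficient with a 95% confidence interval and the number of completers, labelled exploratory.
5. State that no such association is evidence of mediation or of effect modification, and that in the randomized trial the role of adversity would be tested as a treatment-by-ATES interaction.

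The cost is the rewording of one aim and a few sentences on models, using data already planned for weeks 0 and 5. No visit, instrument or participant is added. The downside is a weaker label for the aim and slightly more analysis.
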